## **A. BACKGROUND**

Opioid analgesic drugs have long been the gold standard treatment for perioperative pain relief, playing a crucial role in general anesthesia. Although opioids have a high perioperative analgesic efficacy, they typically cause short-term adverse effects and potentially severe long-term adverse effects as evidenced by the ongoing opioid epidemic in North America (Bohringer et al., 2020; Shanthanna et al., 2021). Opioids can also lead to another problematic condition known as opioid-induced hyperalgesia (OIH), a paradoxical response characterized by increased pain sensitivity in patients using opioids for pain relief (Angst and Clark, 2006; Colvin et al., 2019; Richebé et al., 2018). More specifically, it has been proven that high intraoperative doses of opioids cause hyperalgesia in patients after surgery (Fletcher and Martinez, 2014). Given this, two approaches were explored : opioid-free anesthesia and opioid-sparing anesthesia, employing a combination of analgesics and adjuvants via continuous infusions (Shanthanna et al., 2021).

### **Intraoperative beta-blockers as a opioid-sparing strategy**

The use of esmolol as an adjuvant to general anesthesia has been suggested as an opioid-free potential alternative. Esmolol is an ultra-short acting cardioselective  $\beta_1$ -adrenergic receptor antagonist that plays a crucial role in reducing sympathetic overload induced by numerous perioperative stimuli such as tracheal intubation, intraoperative events, and extubation (Asouhidou and Trikoupi, 2015). Since sympathetic overload generates physiological responses that reflect the patient's pain (Paloheimo et al., 2010), esmolol could serve as a viable alternative to opioids in maintaining hemodynamic stability during general anesthesia (Asouhidou and Trikoupi, 2015). Although esmolol lacks analgesic or anesthetic properties on its own, its combination with propofol or volatile-based anesthesia showed great promise in reducing the intraoperative and postoperative analgesic consumption (Celebi et al., 2014).

Previous studies assessing intraoperative esmolol and its administration based on vital signs have led to inconsistencies and controversies with some studies supporting its use and others disapproving it (Gelineau et al., 2018). However, relying solely on vital signs, such as blood pressure (BP) or heart rate (HR), as a guide for esmolol administration may influence the doses administered as esmolol can lower BP and HR. Thus, this approach might not be ideal as it

could overlook other essential factors and necessitates the adoption of a more comprehensive monitoring system that considers a larger range of parameters.

### **Nociception monitoring as a opioid-sparing strategy**

With the advent of nociception monitoring, new devices can be used, especially the Physiological Monitoring Device PMD-200™. This device offers the multiparameter Nociception Level (NOL) index that integrates five parameters in a dimensionless index : HR, heart rate variation (HRV), photoplethysmographic pulse wave amplitude (PPGA), skin conductance level (SC), number of SC fluctuations . By continuously analyzing the incoming signals with an artificial intelligence algorithm, this monitor provides a real-time index to inform the clinician on the level of nociception felt by the anesthetized patient, thus guiding the administration of opioids. Even if the core signals reflect the activity of the sympathetic nervous system, this monitor has been validated to monitor nociceptive stimuli (Martini et al., 2015; Renaud-Roy et al., 2019; Shahiri et al., 2022), and has been demonstrated to reduce the intraoperative consumption of opioids by 20 to 30% while simultaneously reducing pain and opioids consumption in the PACU.

### **Combining beta-blockers to nociception monitoring**

While it has been demonstrated that chronic usage of beta-blockers does not impair the intraoperative validity of the NOL Index (Bergeron et al., 2022), it remains unclear how acute administration of short-acting cardioselective  $\beta_1$ -adrenergic blocker, such as esmolol, impacts the use of sympathetic system-based nociception monitors. Combining the two opioid-sparing strategies could either act synergistically, or could antagonize their respective benefits.

Therefore, this study aims to evaluate esmolol's perfusion impact during induction and maintenance of general anesthesia, using NOL-guided control of nociception, in adult patients undergoing laparoscopic and lower abdominal surgery, on intraoperative remifentanyl consumption and postoperative pain in the PACU.

## **B. OBJECTIVES & HYPOTHESIS**

### **Primary Objective**

The main objective of the study is to evaluate the impact of continuous intraoperative infusion of esmolol on intraoperative remifentanyl administration in patients undergoing general anesthesia with NOL-guided nociception management.

### **Secondary Objectives**

Secondary objectives cover a wide range of concepts, including the hemodynamic impact of esmolol, the pain profile, and the incidence of opioid-related side effects. More specifically, we aim to :

1. compare NOL Index variation before and after orotracheal intubation and first surgical incision. NOL index will be evaluated 3 minutes after stimulations to record the maximum value and calculate the area under the curve ;
2. compare the mean intraoperative BP and HR;
3. compare the intraoperative requirements and time weighted average of norepinephrine, ephedrine, glycopyrrolate and atropine;
4. compare the total time and time weighted average with NOL value above > 25.
5. To compare the total time and time weighted average of hypotension and/or bradycardia during surgery;
6. compare the time to first analgesic requirement in PACU;
7. compare postoperative morphine equivalent consumption in the post anesthesia care unit (PACU);
8. compare the intensity of pain at rest and under stress, using a verbal rating scale (VRS), from arrival to discharge from PACU;
9. To compare Silvermann Integrated Approach (SIA) Score (combining pain score and opioid consumption);
10. assess postoperative outcomes such as postoperative nausea and vomiting (PONV) and amount of antiemetics used in PACU;
11. compare the time spent in PACU.

## **Hypotheses**

The main hypothesis of this study is to show that patients receiving an intraoperative esmolol infusion during a NOL-guided general anesthesia, will consume a lower amount of intraoperative remifentanyl (mcg.kg-1.h-1) with a reduction of 20 to 30% of intraoperative opioid consumption, without impacting hemodynamic parameters. Upon reproducible nociceptive stimulation such as orotracheal intubation and initial surgical incision, we expect a reduction of the deltaNOL with the administration of esmolol, while still capturing the event on the PMD-200. Finally, once the patient reaches the PACU, we expect a longer time to first opioid, a lower pain score on arrival, a lower opioid consumption, a reduced incidence of PONV, and a shorter PACU stay.

## **C. METHODS**

### **Study design**

The study design is a prospective randomized controlled double-blinded superiority trial, conducted at a single center : Maisonneuve-Rosemont Hospital, part of the Centre intégré universitaire de santé et des services sociaux (CIUSSS) de l'est de l'île-de-Montréal (CEMTL), located in Montreal, Quebec, Canada. The duration of this study is expected to be 1 year, from February 2024 to February 2025.

### **Patient population**

We will screen and aim to recruit consecutive adult patients undergoing laparoscopic lower abdominal surgery expected to last between 60 to 180 minutes.

### **Inclusion criteria**

- Fully consented, ASA 1-3 patients from 18yo to 65yo
- Undergoing laparoscopic surgery associated with sub umbilical mini-laparotomy. Eligible surgeries will be hysterectomy (excluding vaginal approach) and left hemicolectomy, of duration time expected under 180 minutes, under général anesthesia
- No allergy to one of the medications used in this study

## Exclusion criteria

Contraindication to the use of the study drug (esmolol) is an exclusion criterion :

- Hypotension
- Sinus bradycardia
- Sick sinus syndrome
- Second and third degree A-V block
- Pulmonary hypertension
- Right ventricular failure secondary to pulmonary hypertension
- Decompensated heart failure
- Cardiogenic shock
- Nontreated pheochromocytoma
- Known hypersensitivity to esmolol or any of the inactive ingredients of the product
- Allergy to esmolol or other beta blockers (cross-sensitivity is possible)
- Renal dysfunction
- Airway disease such as asthma or COPD
- Thyrotoxicosis
- Myasthenia gravis
- Raynaud's disease or oeripheral circulatory disorder

Other situations leading to exclusion :

- Severe mental impairment
- Chronic use of opioids,  $\beta$ -adrenergic receptors antagonists
- High risk of conversion to laparotomy according to the surgical team (>25%)

Patients will automatically be excluded after recruitment if they withdraw their consent, or if laparoscopy is converted to laparotomy.

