### **Randomization and blinding**

Electronic randomization will be performed by a statistician using a computer-generated randomized sequence with a variable block size unknown to the investigators, and then implemented in a RedCAP™ application. It will be sealed in an opaque envelope and handed to the dedicated research staff not involved in patient care and responsible to prepare the blinded syringe. The envelope will be opened at the patient's entry into the operating ward, after confirming that the surgery will be performed. Once the group is assigned to the patient, the research staff will prepare a syringe containing the randomized solution, either esmolol or saline. Each 10ml ampoule contains 100mg of esmolol. Syringe preparation will depend on the patient's adjusted body weight (ABW) and the expected duration of surgery (DOS) in hour as indicated on the surgical booking request. The number of ampoules required (NA) will be calculated according to the following formula (rounded up to nearest whole number):

$$NA = \frac{ABW \times (0.5 + (1.2 \times DOS))}{100}$$

If a syringe recharge is needed during the surgery, a new blinded syringe containing the same substance as the previous one, will be prepared by the dedicated research staff and brought into the operating room.

The patient, the anesthesiologist, the surgeon, the PACU staff and the research team acting as outcome assessors, will all be blinded to the randomization.

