## **D. ENDPOINTS**

### **Primary endpoint**

The primary endpoint is the intraoperative amount of remifentanyl in mcg.kg-1.h-1, administered between the first surgical incision and its discontinuation at wound dressing.

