### **Data Collection Procedures**

Electronic data from medical monitoring devices, including BIS™ and PMD-200™, will be collected. Before collecting any data, all device times will be time-synchronized. The time of anesthesia induction, intubation, surgical incisions, and other intraoperative events will be manually recorded. This computer gathers all the data electronically and uses the integrated events tag system of the Medasense PMD-200™, or the BetterCare software (provided by Dräger, Lübeck, Germany) connected to the Dräger anesthesia workstation.

All anesthesia and surgery-related events, like the type and amount of vasopressor used, will be recorded separately on a Case Report Form (CRF). The CRF will be built using RedCap software (Vanderbilt University), which will be accessed via electronic tablets by the research team in the operating room. Once the anesthesia is complete and the patient extubated, all the electronic data will be exported.

The data from various monitor devices (anesthesia workstation, ventilator, BIS Index, NOL Index), as well as raw waves form of specific signals (BP, pulse-oximetry, plethysmography, EKG), will be electronically extracted under a unique identification number assigned at randomisation, to a secured, offline research computer, insuring patient anonymization. Patient identity will only be mentioned on the consent form, which will be kept in a locked closet in the Department of Anesthesiology at Maisonneuve-Rosemont Hospital for as long as required by the law (15 years).

Pain intensity is recorded according to a verbal numerical rating scale (0 = absence of pain, and 10 = unbearable pain).

Opioid requirements, pain scores, and post-operative events such as PONV and critical respiratory events will be documented on the PACU record.

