## **E. STATISTICAL PLAN**

### **Sample Size Determination and Power**

Based on a recent unpublished trial (MERK study) recently held at our center focusing on colorectal surgeries, we assumed a mean intraoperative remifentanil consumption of 5.59 mcg.kg-1.h-1 and 7.98, respectively in the intervention and control group, with a combined standard deviation of  $\pm 3.24$ . This data is aligned with recently published international data (Sabourdin et al., 2022). With an alpha risk of 5%, a power of 80.0%, a two-tailed test, and an estimated dropout ratio of 10.0%, it was calculated that 32 patients would be required in each group, to detect a 30% reduction in intraoperative remifentanil administration.

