### **Statistical Methods**

Descriptive statistics will be presented by groups using mean and standard deviation, or median and interquartile range if the distribution is skewed or not normal for continuous parameters (according to the skewness of the distribution of each parameter). Frequency (%) will be used for categorical parameters. According to the nature of the analyzed endpoints, confidence intervals (CIs) between proportions or between means/medians differences will be presented. Missing data will be replaced by the maximum value observed (worst-case scenario). Risk differences or mean differences with 95% confidence intervals will be reported for all outcomes. The alpha value will be set at 0.05 to establish statistical significance. All data will be analyzed by the intention to treat principle. All statistical analysis will be performed using SAS, SPSS software or python programming language via VS Code or Jupyter notebook software.

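### The protocol promises intention to treat, yet it excludes converted patients after allocation, and its withdrawal rules as written end data storage at conversion or NOL-signal failure

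*Protocol*

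**What the plan says.** All references are to the Protocol.

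- **Statistical Methods:** "All data will be analyzed by the intention to treat principle".
- **Exclusion criteria:** "Patients will automatically be excluded after recruitment if they withdraw their consent, or if laparoscopy is converted to laparotomy".
- **Randomization and blinding:** the allocation envelope is opened at the patient's "entry into the operating ward, after confirming that the surgery will be performed".
- **Primary endpoint:** remifentanil in mcg/kg/h, "administered between the first surgical incision and its discontinuation at wound dressing".
- **When and How to Withdraw Patients:** withdrawal covers voluntary departure and also patients who can no longer take part. The examples given are failure to get a stable NOL signal and conversion to laparotomy. Health information is kept in the database.
- **Data Collection and Follow-up for Withdrawn Patients:** no data are stored once a participant has withdrawn.
- **Breach of protocol:** the same two events, together with haemodynamic instability, lead to unblinding and to stopping the study infusion. These events are to be collected and analysed.

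**The concern.** An intention-to-treat comparison keeps every randomised patient in the assigned arm. The protocol promises this and then removes patients because of something that happens during surgery, after the arm has been assigned. For conversion the two instructions cannot both be carried out. NOL-signal failure is not in the exclusion list, but it falls under the withdrawal definition and so under the storage rule.

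Two things are at stake. First, who is in the primary analysis depends on which section the team follows. Second, a storage rule acts during the trial. A later analysis plan can redefine the analysis set, but it cannot recover outcomes that nobody recorded.

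Exclusion after allocation biases the comparison when the excluded patients differ from the rest in remifentanil use and the arms differ in how many are excluded or in how far they differ. Equal loss cannot be presumed for NOL-signal failure, because the Background (Combining beta-blockers to nociception monitoring) calls the effect of acute esmolol on monitors of this kind unclear. Nothing in the document suggests that conversion differs by arm.

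**Working it through.** **1. Timing.** The envelope is opened on arrival, before surgery. Conversion is an intraoperative event, so it follows allocation and falls inside the endpoint window. Breach of protocol requires at least 20 minutes of attempts before NOL failure is declared, so that event may fall before or inside the window.

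**2. The sections side by side.**

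| Event | Exclusion criteria | Withdrawal sections | Breach of protocol | Statistical Methods |
|---|---|---|---|---|
| Conversion | Excluded | Withdrawal; nothing stored afterwards | Collected and analysed | Intention to treat |
| NOL-signal failure | Not listed | Withdrawal; nothing stored afterwards | Collected and analysed | Intention to treat |
| Haemodynamic instability | Not listed | Not listed | Collected and analysed | Intention to treat |

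The conversion row contradicts itself on the analysis set. The first two rows contradict themselves on data collection.

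**3. The protocol's sample size.** Inputs from Sample Size Determination and Power: means 5.59 and 7.98, SD 3.24, two-sided alpha 5%, power 80%, dropout 10%.

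- Difference = 7.98 − 5.59 = 2.39.
- n per arm = 2 × [3.24 × (1.960 + 0.842) / 2.39]² = 28.85, so 29.
- With dropout: 29 × 1.10 = 31.9, so 32 (29 / 0.90 = 32.2 would give 33). The stated 32 is reproduced.

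The allowance corresponds to about 3 patients per arm (10% of 32 = 3.2). With 28.8 left per arm, normal-approximation power is 79.9%.

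**4. Shift from exclusion (assumed values).** Suppose excluded patients use 3.24 mcg/kg/h more than the remaining patients of their own arm, and k1 and k2 of 32 are excluded. The difference in means then shifts by ((k1 − k2) / 32) × 3.24.

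| Split | Shift (mcg/kg/h) | Share of 2.39 |
|---|---|---|
| 3 v 3 | 0 | 0% |
| 4 v 2 | 2/32 × 3.24 = 0.20 | 8.5% |
| 5 v 1 | 4/32 × 3.24 = 0.41 | 16.9% |

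Reversing the split reverses the sign. In simulations with no true effect (20,000 trials, Mann-Whitney at 0.05), the false-positive rate in the remaining set was about 4.6%, 5.5–5.6% and 7.1–7.5%.

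**5. Power when the patients are kept.** Breach of protocol stops the infusion in these patients, so the affected esmolol patients may lose some of the effect. Simulated Mann-Whitney power, with 3 of 32 affected per arm at random:

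| Handling | Normal | Gamma |
|---|---|---|
| Excluded | about 76% | 84–85% |
| Kept, half the effect lost in affected esmolol patients | 76–77% | 83–84% |
| Kept, all the effect lost in them | about 72% | about 80% |

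Keeping these patients gains no power and could cost about 4 points.

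**The case against.** **The data may not be lost.** The storage rule applies only after withdrawal and orders no deletion, the database keeps health information, and Breach of protocol says the events are collected. The rule might have been meant for consent withdrawal alone. The endpoint is also a rate, so one could be computed from incision up to the event. This stands in part. A reader might infer that these patients' records vanish altogether, and the text does not support that. What follows from it is truncation from the event onward, under the reading that the withdrawal definition itself invites. Analysing the events is also not the same as continuing to record outcomes.

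**The missing-data rule could cover it.** "Missing data will be replaced by the maximum value observed (worst-case scenario" might suggest that these patients would receive the maximum dose. The protocol does not say that a shortened record counts as missing, and an excluded patient is not a patient with a missing value. No loss of power should be attributed to that rule here.

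**The dropout allowance covers it.** The sample size includes "an estimated dropout ratio of 10.0" percent, and step 3 shows that this absorbs about that much loss. It answers the question of power, not of comparability.

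**Conversion should be balanced.** The surgeon is blinded and patients with a predicted conversion risk above 25% are screened out. This is fair for conversion, although patients at lower predicted risk remain eligible. It does not address NOL-signal failure.

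**Unblinding.** A reader might see a further contradiction between lifting the blind after these events and the blinding of PACU staff and assessors. The unblinding is an exception triggered by an event, and the text does not say that those staff are told. It is not part of this point.

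**Conclusion.** The protocol is wrong as written. Intention to treat and automatic exclusion of conversions cannot both be followed. The withdrawal sections and Breach of protocol also conflict on what is collected after conversion or NOL-signal failure. If the exclusion and withdrawal rules are obeyed, the primary comparison is not of all randomised patients, and later remifentanil and PACU data are not kept.

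The contradiction is certain; its effect on the result is not. It would be tempting to conclude that the estimate is biased in favour of esmolol, but the protocol gives no rates for either event and supports no particular split between arms. The shifts of 0 to 0.41 mcg/kg/h rest on an assumed excess of 1 SD and assumed splits, and they show scale only. Nor is loss of power the argument, since exclusion costs roughly what the dropout allowance already provides for.

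**What to change.** Reconcile Exclusion criteria, Statistical Methods, the two withdrawal sections and Breach of protocol:

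1. Separate stopping the study infusion or NOL guidance from leaving the study. This need not alter any clinical rule on when either is stopped.
2. Remove conversion and NOL-signal failure as reasons for exclusion from the primary analysis and for ending data storage.
3. Keep recording remifentanil to its discontinuation, and PACU outcomes, unless consent to data use is withdrawn.
4. Analyse all randomised patients in their assigned arm, and report the set without these patients as a sensitivity analysis.
5. If the sponsor prefers a modified set as primary, name and justify it in place of the intention-to-treat statement, with the data still stored.

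**Cost.** Wording, plus a little extra recording. That recording is not automatic: the export list beginning "The data from various monitor devices (anesthesia workstation, ventilator, BIS Index, NOL Index" does not name the remifentanil pump, and "Opioid requirements, pain scores, and post-operative events such as PONV and critical respiratory events will be documented on the PACU record". There is also some dilution, because the study infusion stops in these patients and part of their remifentanil is given outside NOL guidance and after unblinding. Step 5 of the working puts this between no loss of power and about 4 points against exclusion, if 3 of 32 per arm are affected.

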## Recruitment

The research team will assess the elective surgical list of Maisonneuve-Rosemont Hospital's operating room to identify eligible patients at least one week before their scheduled surgery. Potential participants will be contacted by the research team via phone to provide an

explanation of the project. The communication form used during these calls will be approved by the CIUSSS EMTL Research Ethics Committee.

Patients who express interest will receive the information and consent form via email to obtain further details about the study protocol. They will also be informed about the potential risks of esmolol before agreeing to participate.

A thorough review of the patients' medical charts will be conducted to confirm that they meet the inclusion criteria and have no exclusion criteria. Subsequently, the research team will meet the candidates before the surgery to address any questions they may have. If the patients still wish to participate, informed consent will be obtained. Once approved, the patients will sign the consent form and undergo randomization.

